3.5.4. Summary of Accumulation upon Multiple Dosing

Accumulation ratio will be summarized for each dose group in Groups 1-3 (Table 27).

3.5.5. Analysis of Dose Proportionality

The presence of dose proportionality over the range of studied dose levels for Groups 1-3 will be assessed using the exposure parameters AUC_{τ} , C_{max} , and C_{trough} of Dose 1 and at expected steady-state (Dose 5). Analysis will be conducted with the power model as described by Smith et al²:

$$AUC_{\tau} = e^{\alpha} \times dose^{\beta}$$
.

Let ρ be the ratio (highest dose studied / lowest dose studied) and let (L, U) represent the 90% confidence interval for $\hat{\beta}$. In the presence of dose proportionality, $\rho^{\hat{\beta}-1}=1$. Accordingly, using the bioequivalence criteria of the current FDA guidance³, dose proportionality across the studied dose range is concluded when:

$$\Theta_l = 0.8 \le \rho^{L\text{-}1} < \rho^{U\text{-}1} \le 1.25 = \Theta_h.$$

Or, equivalently,

$$1 + \frac{\ln 0.8}{\ln \rho} \le L < U \le 1 + \frac{\ln 1.25}{\ln \rho}.$$

Dose proportionality using C_{max} and C_{trough} will also be assessed using the same approach. Point estimates and 90% confidence intervals for $\hat{\beta}$ will be presented (Table 28). Predicted values from the power model including 90% prediction bands will be overlaid on plots of exposure data (AUC_{\tau}, C_{max}) by dose in mg/kg (Figure 21, Figure 22). Additionally, ANOVA on the log-transformed parameters will be used to construct confidence intervals of the geometric means of dose-adjusted AUC_{\tau} and C_{max} by dose, which will be displayed in Table 29 and plotted side-by-side in order of increasing dosage (Figure 23, Figure 24).

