2.1.2 Human Phase I Safety and Pharmacokinetics

A recent dose escalation study has been performed evaluating 70 healthy adult men and women of non-child bearing potential who were age 18-45 (NCT02234570, DMID 12-0053, unpublished). Seven dose groups were studied (0.5, 1, 3, 7.5, 15, 30 and 60 mg/kg) and each dose group was comprised of 10 subjects of whom eight received study drug and two received placebo. All subjects received a single dose of study drug or placebo and were followed for 14 days for safety and the pharmacokinetics of oxfendazole and metabolites including fenbendazole and oxfendazole sulfone were evaluated in blood and urine. There were no study drug associated serious adverse events identified. Sixteen unsolicited adverse events were experienced by 10 subjects. Six were considered related to the study treatment. Five of the events were mild and included one subject with an increased PR interval 14 days following the dose of study drug, and the remaining events were gastrointestinal events (nausea, loose stools, intestinal gas, and diarrhea, all of which occurred in the 30 or 60 mg/kg dose groups. There was one event, a sore throat that was considered moderate in intensity. Mild to moderate laboratory events were seen in hematology and chemistry tests. There were no patterns identified related to timing of the abnormal laboratory studies or dose of oxfendazole and the placebo group had similar rates of abnormal laboratory values.

The median time of maximum concentration (T_{max}) occurred at 2 hours and the geometric mean maximum concentration (C_{max}) ranged from 943.9-6768.4 ng/mL. The exposure was non-linear, plateauing at 15 mg/kg. The half-life ($t_{1/2}$) was consistent between groups and ranged from 8.5-11 hours. The overall fraction of drug excreted in the urine was very low and the geometric mean AUC_{0-t} for the sulfone metabolite was 11.5-15% of oxfendazole AUC_{0-t} while fenbendazole AUC_{0-t} was less than 1% of oxfendazole AUC_{0-t} for each dose group.

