11.1 Study Hypotheses

The primary objective of this study will be assessed through estimation rather than hypothesis testing, as this is a Phase I study with small sample sizes. The study includes eight subjects in each of the first three cohorts and twelve subjects in the fourth cohort.

The secondary objective of defining the multi-dose kinetics of oxfendazole will be assessed using a descriptive analysis with no formal hypothesis test. For the secondary objective of the determination of the effect of food on the kinetics of oxfendazole, equivalence between the fasting (water is permitted) and fed conditions will be tested using 90% confidence intervals and 80-125% equivalence limits for AUC_{0-∞}, AUC₀₋₂₄, and C_{max} in accordance with FDA guidance.

<http://www.fda.gov/downloads/RegulatoryInformation/Guidances/UCM126833.pdf>

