11.2 Sample Size Considerations

The sample sizes were selected to obtain preliminary safety information on a small cohort of subjects before proceeding to larger trials. In this Phase 1 study, we are concerned with rates of adverse events, which theoretically could occur due to oxfendazole treatment. The dosing regimens with respective sample sizes are described in Table 4 below:

Table 4. Sample sizes for each dose regimen

Cohort	Dose Regimen	Sample size
1	3 mg/kg daily for 5 days	8
2	7.5 mg/kg daily for 5 days	8
3	15 mg/kg daily for 5 days	8
4	Single dose of 3 mg/kg after fasting (water is permitted) with cross-over to single dose of 3 mg/kg after high-fat meal.	12

The study will produce preliminary estimates of adverse event rates for each dosing regimen. The true adverse event rates within each dosing regimen are unknown. The below table displays probabilities of observing at least one adverse event within a cohort assuming different true underlying event rates and sample sizes. For example, if an adverse event has a true rate of 0.20, then the probability of observing at least one adverse event among 8 subjects is 0.83. There is a 0.93 probability of observing the event among 12 subjects. The probabilities were calculated using R statistical software, version 3.2.2.

Table 5. Probabilities of observing adverse events for various event rates and sample sizes

True Rate of Adverse Event	Probability of observing at least one adverse event within a cohort	
	Among 8 subjects	Among 12 subjects
0.01	0.08	0.11
0.05	0.34	0.46
0.08	0.49	0.63
0.10	0.57	0.72
0.15	0.73	0.86
0.20	0.83	0.93

With 12 total participants to assess the secondary objective of the determination of the effect of food on the kinetics of oxfendazole, the power is 80% when the coefficient of variation is less than 0.175 and 64% when the coefficient of variation is 0.2.

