| AR Estimation Method | | Group 1 (3 mg/kg) | Group 2 (7.5 mg/kg) | Group 3 (15 mg/kg) |
|--|--------|----------------------|------------------------|-----------------------|
| $AR = \frac{AUC_{\tau, Dose 5}}{AUC_{\tau, Dose 1}}$ | N | X | X | X |
| $AR = \frac{AUC_{\text{r. Decol}}}{AUC_{\text{r. Decol}}}$ | Mean | X.X | X.X | X.X |
| t, bose i | SD | X.X | X.X | X.X |
| | Min | X.X | X.X | X.X |
| | Median | X.X | X.X | X.X |
| | Max | X.X | X.X | X.X |
| | CV % | X | X | X |
| | GM | X.X | X.X | X.X |
| C | N | X | X | X |
| $AR = \frac{C_{\text{max, Dose 5}}}{C_{\text{max, Dose 1}}}$ | Mean | X.X | X.X | X.X |
| max, Dose 1 | SD | X.X | X.X | X.X |
| | Min | X.X | X.X | X.X |
| | Median | X.X | X.X | X.X |
| | Max | X.X | X.X | X.X |
| | CV % | X | X | X |
| | GM | X.X | X.X | X.X |
| 1 | N | X | X | X |
| $AR = \frac{1}{1 - e^{-\lambda_Z \tau}}$ | Mean | X.X | X.X | X.X |
| 1-e ² | SD | X.X | X.X | X.X |
| | Min | X.X | X.X | X.X |
| | Median | X.X | X.X | X.X |
| | Max | X.X | X.X | X.X |
| | CV % | X | X | X |
| N-4 1 | GM | X.X | X.X | X.X |

Note: λ_Z from Dose 5 is used to estimate AR.

Table 28: Dose Proportionality Power Model Estimates: Groups 1-3

| | Exposure Parameter | $\widehat{oldsymbol{eta}}$ | 90% CI | Conclusion ¹ | |
|--------|---------------------------------------|----------------------------|----------------|-------------------------|--|
| | C _{max} (ng/mL) | X.XXX | (x.xxx, x.xxx) | Proportional | |
| Dose 1 | C _{trough} (ng/mL) | X.XXX | (x.xxx, x.xxx) | Proportional | |
| | $AUC_{\tau} (ng \cdot \frac{hr}{mL})$ | x.xxx | (x.xxx, x.xxx) | Proportional | |
| | C _{max} (ng/mL) | X.XXX | (x.xxx, x.xxx) | Not Proportional | |
| Dose 5 | C _{trough} (ng/mL) | X.XXX | (x.xxx, x.xxx) | Not Proportional | |
| | $AUC_{\tau} (ng \cdot \frac{hr}{mL})$ | x.xxx | (x.xxx, x.xxx) | Inconclusive | |

¹Based on comparison of 90% CI to limits of (x.xxx, x.xxx) in accordance with FDA-recommended bioequivalence criteria

Table 29: Geometric Mean Dose-adjusted Exposure by Dose Group

| | | Geometric Mo | ean of Dose-adjusted Exp | oosure (95% CI) | |
|--------|--|-------------------|--------------------------|--------------------|--|
| | Exposure Parameter | Group 1 (3 mg/kg) | Group 2 (7.5 mg/kg) | Group 3 (15 mg/kg) | |
| Dose 1 | | x.x | X.X | X.X | |
| | $C_{\text{max}}\left(\frac{\text{ng/mL}}{\text{mg/kg}}\right)$ | x.x | x.x | x.x | |
| | 3, 3 | x.x | X.X | X.X | |
| | , , | x.x | X.X | X.X | |

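### At 8 subjects per dose the dose-proportionality criterion can seldom be met unless residual variability is low, and its single slope cannot show at which dose step proportionality is lost

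*SAP*

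**What the plan says.** SAP 3.5.5 fits a power model to AUCτ, Cmax and Ctrough at Dose 1 and Dose 5 in Groups 1–3. It lets (L, U) "represent the 90% confidence interval for" the slope and sets limits "using the bioequivalence criteria of the current FDA guidance", so 0.80 to 1.25 applies to the dose-normalised exposure ratio between the top and bottom doses. The decision sentence reads "dose proportionality across the studied dose range is concluded when" both ends of the interval meet those limits.

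The Table 28 shell gives six slopes, each with its 90% interval and a one-word conclusion, described as made "in accordance with FDA-recommended bioequivalence criteria". The shell shows three labels: Proportional, Not Proportional and Inconclusive. Section 3.5.5 defines only the first.

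Table 29 adds dose-adjusted geometric means with 95% intervals for each dose group, and Figures 23–24 plot dose-adjusted exposure by dose. No between-dose ratio is planned.

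Protocol 11.1 says: "The secondary objective of defining the multi-dose kinetics of oxfendazole will be assessed using a descriptive analysis with no formal hypothesis test". Protocol 11.4.4 nevertheless plans to examine dose proportionality by ANOVA or the power model, taking an exponent near 1 as linear. It sets no equivalence limits.

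**The concern.** Limits of 0.80–1.25 are demanding for a parallel-group slope estimated from 24 subjects, because the residual contains between-subject as well as within-subject variation. Neither document states an assumed CV or a power for this rule. The only CVs given belong to the Group 4 crossover: "the power is 80% when the coefficient of variation is less than 0.175 and 64% when the coefficient of variation is 0.2".

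Two things are at stake. A reader of Table 28 may not realise that a verdict other than Proportional can simply reflect sample size. And the earlier single-dose study already points to a loss of linearity: "The exposure was non-linear, plateauing at 15 mg/kg". Since 15 mg/kg is the top dose here, a reader will want to know which dose step departs from proportionality. One slope averages over both steps.

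**Working it through.** **Calibration.** The documents give no figure for this rule, so I first reproduced the protocol's crossover power. The method was two one-sided tests with n = 12, 10 df, true ratio 1 and σ = √ln(1 + CV²). It gives 79.9% at CV 0.175 and 64.4% at CV 0.20, against the stated 80% and 64%.

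**Inputs.** Doses are 3, 7.5 and 15 mg/kg with 8 subjects each (Protocol 11.2, SAP 2.1). The interval is 90% with limits 0.80–1.25 (SAP 3.5.5). I assume log-normal exposure with equal variance across doses.

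**Limits on the slope.** The dose ratio is 15/3 = 5, and ln(1.25)/ln(5) = 0.2231/1.6094 = 0.1386. The limits are therefore 0.861 to 1.139.

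**Ceiling on the estimated CV.**
- Deviations of ln(dose) from their mean are −0.842, 0.074 and 0.768. So Sxx = 8 × (0.709 + 0.006 + 0.589) = 10.43 and √Sxx = 3.229.
- The interval half-width is t(0.95, 22 df) × s/√Sxx = 1.717 × s/3.229.
- It fits only if s ≤ 0.1386 × 3.229/1.717 = 0.2607, that is CV = √(exp(0.2607²) − 1) = 26.5%.
- The ceiling stays at 26.5% if sex is kept in the model under SAP 3.5.2 (21 df). It falls to 25.5% if one subject in the 3 mg/kg group is not evaluable.

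**Chance of Proportional when the true slope is exactly 1.** For a given s, the estimate must fall within w = 0.1386 − 1.717 s/3.229 of 1, and its standard error is σ/3.229. I averaged this probability over the chi-square distribution of s² and confirmed it by simulation.

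| True residual CV | Chance of Proportional |
|---|---|
| 15% | 79% |
| 17.5% | 61% |
| 20% | 42% |
| 25% | 14% |
| 26.5% | 9% |
| 30% | 3% |
| 40% | 0.1% |

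A chance of 80% needs a true CV of about 15% or less. To show how CVs combine: if within-subject CV were 0.20, a between-subject CV of about 17% would bring the total to 26.5%, since ln(1 + 0.265²) − ln(1 + 0.20²) = 0.068 − 0.039 = 0.029 and √(exp(0.029) − 1) ≈ 0.17.

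**What the rule can still detect.** Take a full plateau above 7.5 mg/kg as an illustration. The expected slope is (−0.842 × ln 3 + (0.074 + 0.768) × ln 7.5)/1.303 = 0.59. The interval lies wholly outside the limits in 81%, 64% and 50% of simulated trials at CV 30%, 40% and 50%, against 0.2%, 0.5% and 1.1% under exact proportionality.

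**What locates the step.** Under the same plateau the true dose-normalised ratios are 1.0 for 7.5 v 3 mg/kg and 7.5/15 = 0.5 for 15 v 7.5 mg/kg. At CV 30% the 90% interval for the 15 v 7.5 ratio lies wholly below 0.80 in 93% of trials. The slope of 0.59 carries no such information.

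**The case against.** A reader might infer that the verdict is almost fixed in advance. The documents do not support that. The 26.5% is a ceiling on the estimated CV, not a cliff in the true CV, and no between-subject CV is given. At true CVs of 17.5% to 20% the outcome is open. Only one label drops out at higher CVs, and the rule still separates a marked plateau from proportionality.

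Nor are 0.175 and 0.20 a floor for the residual CV. They are what-if inputs to a power statement, not measured oxfendazole variability. A parallel-group residual would be expected to exceed the within-subject one, but by how much is unknown.

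It is also tempting to say that a failed criterion must be reported as non-proportionality. The Table 28 shell already prints Inconclusive; what is missing is the line between it and Not Proportional.

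Trough timing might seem to settle the matter for Ctrough at Dose 5. That depends on the Day 6 window, which is ±6 h in SAP 2.3 but +6 h only in Protocol 7.3 and Appendix A. With draws spread uniformly and half-lives of 8.5–11 h, timing adds a log-SD of 0.22–0.28 in the first case but 0.11–0.14 in the second.

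Protocol 2.1.2 does not say that exposure is flat between 7.5 and 15 mg/kg, so the plateau above is only a test case. A clash with Protocol 11.1 is a thin argument, because Protocol 11.4.4 itself plans the power model.

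Finally, the slope with its interval and the dose-adjusted means are already planned, the study is declared exploratory, and no decision in either document depends on Table 28. All of this stands and limits the point to an improvement. It does not supply the missing between-dose comparison.

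**Conclusion.** The concern holds in limited form. The 26.5% ceiling follows exactly from the planned design and the SAP's own limits. A drug with a true slope of exactly 1 would be called Proportional in 79% of trials at a true residual CV of 15%, 42% at 20% and 3% at 30%. Which figure applies rests on a CV that the documents do not give, together with log-normal exposure and all 24 subjects evaluable.

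The verdict column remains informative about marked departures. The more useful gap is that nothing planned estimates the change in dose-normalised exposure from one dose level to the next. The point is a low-cost improvement to a secondary, exploratory analysis, not an error that invalidates it.

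**What to change.** In SAP 3.5.5 and the Table 28 and 29 shells:

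- Keep the slope and its 90% interval in Table 28.
- From the ANOVA already planned for Table 29, add ratios of dose-normalised geometric means for 7.5 v 3, 15 v 7.5 and 15 v 3 mg/kg, with 90% intervals.
- Report the largest dose ratio over which the 0.80–1.25 criterion is met, 1.25^(1/max(1 − L, U − 1)). With an estimated slope of exactly 1 this is 8.3, 4.2, 3.0 and 2.4 at an estimated CV of 20%, 30%, 40% and 50%. Values above 5 go beyond the doses studied and should be shown as at least 5.
- If the verdict column stays, use Not Proportional only when the whole interval lies outside 0.861–1.139, and Inconclusive when it overlaps a limit. Footnote that Proportional cannot be reached at 8 per dose if the estimated residual CV exceeds 26.5%.

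This takes SAP wording and two table shells, with no new data, subjects or model. The downside is a few more exploratory estimates, unadjusted for multiplicity, and a less clear-cut verdict. The added ratios will not often prove proportionality either. At an estimated CV of 30% (s = 0.294) an observed ratio of 1 has a 90% interval of about 0.78 to 1.29, from a log half-width of 1.721 × 0.294 × √(2/8) = 0.253. Their use is to show where a large departure lies.

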3.5.6. Analysis of Changes in T_{max} by Dose Number and Dose Level

Shift in T_{max} between Dose 1 and Dose 5 for Groups 1, 2 and 3 will be tested using the Wilcoxon signed-rank test procedure. Point estimates of the shift (the Hodges-Lehmann estimator) and associated 90% confidence intervals will be provided (Table 30). A test for any difference in T_{max} among the three studied dose levels will be performed using the Kruskal-Wallis one-way ANOVA on ranks.

3.5.7. Analysis of Food Effect

Determination of the effect of food on the kinetics of oxfendazole in Group 4 will be conducted in accordance with current FDA guidance^{3,4}. Key exposure parameters (AUC_(0-∞), AUC_(0-last), and C_{max}) will be log-transformed and analyzed using the following mixed effects model for Y_{ijk} , the log-transformed exposure parameter observed for the *i*th condition (fed/fasted) for the *k*th subject in period *j*:

$$Y_{ijk} = \mu + \pi_j + \lambda_{d(i,j)} + \tau_{d(i,j)} + s_k + \varepsilon_{ijk}$$

where μ is an intercept; π_j is a fixed effect associated with period j; λ_i is a fixed effect associated with the condition i, $\tau_{d[i,j]}$ is a fixed effect associated with the interaction of period j and condition i; and s_{ik} is a random effect associated with the kth subject with mean 0 and variance σ_s^2 , and e_{ijk} is a random error term with mean 0 and variance σ_e^2 .

The model will be fit using REML in SAS PROC MIXED. Point estimates and 90% confidence intervals for the mean difference between fed and fasted conditions will be constructed for each log-transformed exposure parameter. SAS code will be similar to:

PROC MIXED;

CLASS PERIOD CONDITION SUBJECT;

MODEL LCMAX = PERIOD CONDITION PERIOD*CONDITION / DDFM=KR;

RANDOM SUBJECT;

LSMEANS CONDITION / ALPHA=0.1 PDIFF CL;

RUN:

Point and interval estimates of the mean difference in log-transformed exposure parameters will then be back-transformed to obtain point estimates and 90% confidence intervals for the ratio of geometric means of the parameters. Equivalence between the fasting and fed conditions will be based on whether the 90% confidence interval for the ratio of the population geometric mean of the parameter measured from the 2 conditions is contained in the interval [0.80, 1.25].

In addition, for each exposure parameter, the intrasubject coefficient of variation (CV_W) will be calculated to provide an estimate of the variability in exposure within the same subject, when the subject is administered one dose of study product on two separate occasions.

For normally distributed data with mean μ and variance σ^2 , coefficient of variation is defined as:

$$CV = \sqrt{Var\left(\frac{X - \mu}{\mu}\right)} = \frac{\sigma}{\mu} = \frac{\sqrt{Var(X)}}{E(X)}$$

If X is instead distributed log-normally (i.e., Y = log(X) is normally distributed with mean μ and variance σ^2), then:

$$E(X) = \exp\left(\mu + \frac{\sigma^2}{2}\right)$$

$$Var(X) = [exp(\sigma^2) - 1] exp(2\mu + \sigma^2)$$

The coefficient of variation can be written in terms of σ^2 as:

$$CV = \frac{\sqrt{Var(X)}}{E(X)} = \frac{\left[\sqrt{exp(\sigma^2) - 1}\right] \exp\left(\mu + \frac{\sigma^2}{2}\right)}{\exp\left(\mu + \frac{\sigma^2}{2}\right)} = \sqrt{exp(\sigma^2) - 1}$$

Thus, the intrasubject coefficient of variation can be estimated from the model on log-transformed data as:

$$\widehat{CV_W} = \sqrt{\exp(MSE) - 1}$$

where MSE is the residual mean squared error from the model. Results from the statistical analysis of food effect will be shown in Table 31.

Distributional assumptions and homoscedasticity will be assessed by residual plots and/or other graphical diagnostics. Alternative analyses will be considered if assumptions are violated.

Food effect on T_{max} will be assessed with the Wilcoxon signed-rank test procedure. The Hodges-Lehmann estimator (pseudomedian) for the difference in T_{max} between fed and fasted conditions will be reported, as well as the associated 90% confidence interval will be displayed in Table 32. Potential differences in T_{max} due to sequence effects will be explored graphically.

3.6. Comparison of Current Pharmacokinetic Results to Pharmacokinetic Results from Previous Studies

Not applicable.

